8.3. Missing Data

The primary method to impute the missing values will be as follows:

Continuous Endpoints: For continuous secondary endpoints (except EQ-5D, HADS) during treatment period, the MI under MAR assumption approach and the MMRM approach will be used to handle the missing data.

Binary Endpoints: All missing values will be treated as a non-responder for the binary endpoints for primary, key secondary and secondary endpoints. To assess the robustness of non-responder analysis for primary and key secondary endpoints, a tipping point analysis will be performed. The MI under MAR assumption, last observation carried forward (LOCF) approach, and observed case (OC) approach will be used as sensitivity analysis to impute the missing values for the primary and key secondary endpoints. If applicable, the continuous response will be imputed first, and the response will then be categorized.

Use of rescue therapy: All efficacy data, except OC, will be treated as treatment failure. Binary endpoints will be based on the underlying values and continuous variables will be imputed using the worst case score (questionnaires) or worst case value (diary data), on or after rescue therapy is used, independent if visit was attended or not. This procedure will be completed before imputing missing data under different assumptions (i.e., non-responder, LOCF, MI under MAR/MNAR). A different approach will be applied for MMRM analysis where data on or after rescue therapy will be considered as missing before applying MMRM analysis.

In OC analysis, no observed data after subject has received rescue treatment will be excluded. There will be no imputations for missing data.

Adverse events and concomitant medications/procedures: Missing assessment times will have imputed times for the purposes of assessing treatment emergence for AEs or classifying medications/procedures into prior/concomitant. However, the assessment date and time (start date, stop date, and time if collected from CRF) without imputation will be presented in the listings.

For the start of a concomitant medication/procedure or AE:

- Only the year is reported: If the subject received the first study drug dose in the year reported, then the date of the first dose of study drug will be used as the start date; otherwise, January 1 of the year reported will be used as the start date.

This document is confidential.

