- The month and year are reported: If the subject received the first study drug in the month and year reported, then the date of the first dose of study drug will be used as the start date; otherwise, the first day of the month and year will be used as the start date.
- The time is collected but missing: If the start date is the same as the date the subject started receiving study drug, then the time of the first dose of study drug will be used as the start time; otherwise, 00:00 will be used as the start time.

For the end of a concomitant medication/procedure or AE:

- Only the year is reported: The earlier between December 31 of the year reported and the date of the last study contact with the subject will be used as the stop date.
- The month and year are reported: The earlier between the last date of the month and year reported and the date of the final contact with the subject will be used as the stop date.
- The time is collected but missing: 23:59 (or 23:59:59 if collected up to seconds) will be used as the stop time.

If an AE has the start date completely missing and the stop date on/after the first dose date of study drug, this AE will be considered as treatment emergent (TEAE).

If a medication/procedure has the stop date completely missing, this medication/procedure will be considered as ongoing and concomitant. If the start date of a medication/procedure is completely missing and impossible to identify different by stop date, this medication will be considered as concomitant.

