13.1. Adverse Events

AEs will be coded using MedDRA Version 25.0.

Treatment-emergent AEs (TEAEs), defined as those AEs occurring after the first administration of study treatment until the last study visit, will be tabulated in frequency tables by System Organ Class (SOC) and Preferred Term (PT) based on the Medical Dictionary for Regulatory Activities for treatment and follow-up periods. Missing date information will be handled using the algorithm described in [Section 8.3](#).

TEAEs during treatment period are defined as AEs with onset date on or after the first dose date till 4 weeks after the last treatment or early discontinuation date whichever is earlier. TEAEs during follow-up period are defined as AEs with onset date post treatment period (4 weeks after the last treatment or early discontinuation date, whichever is earlier) to follow-up visit date.

AEs will be summarized using the number and percent of subjects reporting each SOC and PT and sorted alphabetically by SOC and by descending frequency of PT within SOC.

Subjects who experienced multiple events within the same SOC will be counted once in the SOC summary. Subjects who experienced multiple occurrences of events with the same PT will be counted once in the PT summary.

When summarizing by causality or maximum severity, if a subject experiences more than 1 occurrence of the same AE, the occurrence with the greatest severity and the closest association with the study drug will be used in summary tables. TEAEs related to study drug/study procedure are those that are identified as reasonable possibility. If relationship or severity are missing, the event will be considered as AE related to study drug/study procedure or severe AE.

An AESI is a noteworthy treatment-emergent event for the study drug that should be monitored closely and reported promptly. An AESI can be either serious or non-serious. Based on the potential risks of Nemolizumab and the risks associated with biologics in general (i.e., class effects), the following AEs will be considered as AESIs:

- Injection-related reactions,
- Newly diagnosed asthma or worsening of asthma,
- Infections,
- Peripheral oedema: limbs, bilateral,
- Facial oedema
- Elevated ALT or AST ($> 3 \times$ ULN) in combination with elevated bilirubin ($> 2 \times$ ULN).

The following summary tables for TEAEs will be presented for all TEAEs (i.e., TEAE all causalities) and study drug related TEAEs separately by treatment period and follow-up period.

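### Partial adverse-event start dates are set to the first-dose date without checking the stop date, so an event that ended before dosing can be counted as treatment-emergent

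*SAP*

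**What the plan says.** SAP Section 8.3 gives the date rules and their purpose: "Missing assessment times will have imputed times for the purposes of assessing treatment emergence for AEs", and likewise for sorting medications and procedures into prior and concomitant. Three of its rules matter for an adverse event (AE).

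- Year only, with first dose in that year: "then the date of the first dose of study drug will be used as the start date"; in any other year it is 1 January.
- Month and year: "If the subject received the first study drug in the month and year reported, then the date of the first dose of study drug" becomes the start; in any other month it is the first of that month.
- No start date at all: "If an AE has the start date completely missing and the stop date on/after the first dose date of study drug", the event is a TEAE.

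The first two rules do not mention the stop date. The third depends on it.

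Section 13.1 describes TEAEs in two ways. In general terms they are events that arise once the first administration has been given, up to the last visit. For the treatment-period tables the rule is by onset: "TEAEs during treatment period are defined as AEs with onset date on or after the first dose date". It adds "Missing date information will be handled using the algorithm described in" Section 8.3.

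Section 8.3 also says that listings show the dates without imputation. Section 13 starts safety assessment at informed consent, Section 8.2 allows a screening period of up to 4 weeks, and Section 13.1 plans a separate listing of pre-treatment AEs.

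**The concern.** Setting a partial start to the first-dose date is a sound conservative convention when it is unknown whether the event began before or after dosing. It has no purpose when the stop date shows that the event was over before dosing. The two partial-date rules do not separate these situations.

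There are two consequences. The derived start can fall after the stop, which is impossible. And because Section 13.1 works on onset date, the event moves from pre-treatment to treatment-emergent. It would then enter the TEAE tables and the numerator of the exposure-adjusted incidence rates. Infections are an AESI category, so a screening infection that had already resolved could be tabulated as a treatment-emergent AESI.

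The plan is also inconsistent with itself: the same pre-dose stop date does not meet the TEAE rule when nothing is known about the start, but gives a TEAE when the month or year is known.

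**Working it through.** The SAP gives no figure to reproduce. The check applies its rules as written to example events. The first-dose date, 20 March 2021, and all event dates are assumptions chosen for illustration.

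Rules used:

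- Start, month and year reported: first-dose date if the month and year match first dose, otherwise the first of that month (Section 8.3).
- Start, year only: first-dose date if the year matches first dose, otherwise 1 January (Section 8.3).
- Stop, month and year reported: the earlier of the last day of that month and the final contact (Section 8.3).
- TEAE if start is on or after first dose (Section 13.1). With no start date at all, TEAE if stop is on or after first dose (Section 8.3).

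| Case | Reported start | Reported stop | Derived start | Derived stop | Start after stop? | TEAE? |
|---|---|---|---|---|---|---|
| 1 | Mar 2021 | 12 Mar 2021 | 20 Mar 2021 | 12 Mar 2021 | yes | yes |
| 2 | 2021 | 12 Mar 2021 | 20 Mar 2021 | 12 Mar 2021 | yes | yes |
| 3 | 2021 | Feb 2021 | 20 Mar 2021 | 28 Feb 2021 | yes | yes |
| 4 | Feb 2021 | 12 Mar 2021 | 1 Feb 2021 | 12 Mar 2021 | no | no |
| 5 | Mar 2021 | Mar 2021 | 20 Mar 2021 | 31 Mar 2021 | no | yes |
| 6 | Mar 2021 | 2 Apr 2021 | 20 Mar 2021 | 2 Apr 2021 | no | yes |
| 7 | none | 12 Mar 2021 | none | 12 Mar 2021 | not applicable | rule not met |

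Cases 1 to 3 show the fault. In cases 1 and 2 the derived start is 20 − 12 = 8 days after the recorded stop. Case 3 shows that a partial stop date can place the event before dosing just as clearly as a full one.

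Cases 4 to 6 mark the limits. A partial start outside the period of first dose is handled correctly (case 4). Where the stop may be, or is, on or after first dose, the event is a TEAE under the ordinary conservative convention and no dates are inverted (cases 5 and 6).

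Case 7 against cases 1 and 2 shows the inconsistency: the stop date is the same, and the treatment-emergence result differs only because part of the start date is known.

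With a stop-date condition added, the derived start becomes 1 March 2021 in case 1 and 1 January 2021 in cases 2 and 3. None of the three is then a TEAE and none has a start after its stop. Cases 4 to 6 do not change.

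**The case against.** Four points can be made for the current text.

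- **The general description may settle the matter.** An event that ended before dosing did not arise after first administration, imputation serves only to decide treatment emergence, and a pre-treatment listing exists. A programmer could reasonably classify such an event as pre-treatment. This stands in part: the text permits the misclassification, and it is too strong to infer that every such event will certainly be misclassified. It does not remove the problem, because the rule for the treatment-period tables uses onset date and refers to Section 8.3 for missing dates. A literal implementation gives a TEAE.
- **The convention is deliberately conservative.** This holds for uncertain events such as cases 5 and 6. It does not hold where the stop date has already resolved the uncertainty.
- **Impossible date pairs will not be displayed.** This stands. A reader might infer that the report's listings would show events starting after they end, but listings carry unimputed dates. The inversion stays in the derived data. What would show is a listed stop before first dose for an event tabulated as a TEAE, which at least makes the error detectable.
- **The effect is small and even-handed.** This stands too. The rule is identical in both arms, it can only add TEAEs, and Section 13.1 plans no hypothesis test on AEs.

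**Conclusion.** The gap is real and minor. Section 8.3, read literally with the onset rule in Section 13.1, turns an AE with a pre-dose stop into a TEAE, and nothing else in the SAP corrects this.

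Two conditions must both hold: a partial start in the same year, or the same month and year, as first dose; and a stop date, recorded or imputed, before first dose. A reader might infer that all screening-period AEs with a partial start in that period are wrongly counted. The SAP does not support that: those that are ongoing, or that stop on or after first dose, are TEAEs under the plan's intended convention and remain so after the fix.

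The SAP gives no count of such events. That they are few is an assumption, based on the screening period of up to 4 weeks and the need for both conditions. No efficacy result is affected, and nothing in the SAP suggests that a comparison between the arms would turn on it.

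**What to change.** In both partial-date bullets of Section 8.3, use the first-dose date only if the stop date (recorded, or imputed when partial) is missing, ongoing, or on or after first dose. Otherwise use the first day of the reported month or year, never later than the stop date. The condition has to include imputed stops, or case 3 would remain.

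State that the same condition applies to medications and procedures, which share these bullets. Sections 9.4 and 9.5 already define prior procedures and medications by a stop before the first treatment. At present, an item stopped before first dose could be prior by its stop date and also meet the start criterion for concomitant by its imputed start.

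The cost is one clause in the SAP and the matching line in the date-derivation program. No new data are needed, and events whose timing is truly uncertain are still counted as TEAEs.

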8.4. Visit Windows

Efficacy by-visit summaries will use the analysis visit. All visits (Scheduled, Unscheduled and early termination visits) will be windowed based on the analysis visit window in [Table 8-1](#) which is based on study day. If multiple measurements are taken within the same window, the one taken closest to the target study day will be used for the analysis. If there are multiple measurements with same difference from target day, the later assessment should be used for the analysis.

Table 8-1: Analysis Visit Window

Analysis Visit	Target Study Day	Visit Window for IGA, PAS, PN associated Pain frequency and intensity	Visit Window for PGIS-P, PGIS-SD, PGIC-P, PGIC-SD, PGAD, PGAT, EQ-5D, HADS	Visit Window for DLQI
Baseline	1	≤ 1	≤ 1	≤ 1
Week 1	8	NA	2 to 60	NA
Week 4	29	2 to 42	NA	2 to 60
Week 8	57	43 to 70	NA	NA
Week 12	85	71 to 98	NA	NA
Week 16	113	99 to 126	61 to 154	61 to 154
Week 20	141	127 to 154	NA	NA
Week 24	169	155 to 210	155 to 210	155 to 210

This document is confidential.

Week 32 Follow-up	225	211 to 238	NA	NA
-------------------	-----	------------	----	----

All daily diary efficacy data will be classified into analysis visits as described in [Table 8-2](#) considering the data during the 7 days immediately preceding the target day of analysis visit.

Analysis visit of diary (ePRO) data will be defined depending on the data collection as below.

Diary data assessed within the extended timeframe below will be considered for analysis. The following rule will be applied for post-treatment assessments only.

- Evening assessment (PP/AP NRS) recorded from 17:00:00 to 00:59:59
- Morning assessment (SD NRS, morning sleep diary) recorded from 5:00:00 to 17:59:59

Consecutive daily assessment:

For the evening assessments (PP NRS, AP NRS), the daily data collected up to Week 24 will be classified into analysis visits considering the data during the 7 days immediately preceding the target study day of analysis visit. Similarly, for the morning assessment (SD NRS, morning sleep diary), the 7 days data up to the target study day will be classified into analysis visit. Details of the analysis visit window are in Table 8-2 below.

Table 8-2: Analysis Visit Window for Evening and Morning Assessments*

Analysis Visit	Target Study Day of Analysis Visit	Visit Window for evening assessment (PP NRS, AP NRS)	Visit Window for morning assessment (SD NRS, morning sleep diary)
Baseline ^a	1	-7 to -1	-6 to 1 before dosing
Week 1	8	1 to 7	2 to 8
Week 2	15	8 to 14	9 to 15
Week 3	22	15 to 21	16 to 22
Week 4	29	22 to 28	23 to 29
Week 5	36	29 to 35	30 to 36
Week 6	43	36 to 42	37 to 43
Week 7	50	43 to 49	44 to 50
Week 8	57	50 to 56	51 to 57
Week 9	64	57 to 63	58 to 64
Week 10	71	64 to 70	65 to 71
Week 11	78	71 to 77	72 to 78
Week 12	85	78 to 84	79 to 85
Week 13	92	85 to 91	86 to 92
Week 14	99	92 to 98	93 to 99
Week 15	106	99 to 105	100 to 106
Week 16 ^b	113	106 to 112	107 to 113
Week 17	120	113 to 119	114 to 120
Week 18	127	120 to 126	121 to 127
Week 19	134	127 to 133	128 to 134
Week 20	141	134 to 140	135 to 141
Week 21	148	141 to 147	142 to 148
Week 22	155	148 to 154	149 to 155
Week 23	162	155 to 161	156 to 162

This document is confidential.

Week 24	169	162 to 168	163 to 169
---------	-----	------------	------------

^a If there are less than 4 non-missing assessments within last 7 days prior to the first dose, the interval lower bound will be extended up to 7 additional days, one day at a time, to obtain the most recent 4 non-missing values. The extension will not be applied for the sensitivity analysis by using a minimum of 2 (or 3) daily scores out of the 7 days.

^b If there are less than 4 assessments during Week 16 visit window, upper bound of the visit window (106 - 112) or (107 - 113) will be extended for 5 additional days. If there are still less than 4 assessments after extending upper bound of the visit window, lower bound of the visit window will be extended for another 5 days until 4 assessments are reached.

* For diary data, if the intake date of rescue therapy is before and on the last day of the weekly visit window, this week will be treated as treatment failure except for OC analysis and the weekly average will be imputed using the worst case value, see [Section 8.3](#). For MMRM analysis, values will be considered as missing.

Safety and pharmacokinetics data will not be windowed for by-visit summary. i.e., scheduled visit data will be used for analysis.

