- SD NRS and sleep diary questions to be recorded by subjects once daily in the morning and if possible, within 1 hour of getting out of bed (Visit 1/Screening through Visit 8/Week 24). PP NRS and AP NRS to be recorded by subjects once daily in the evening (Visit 1/Screening through Visit 8/Week 24), beginning after the screening visit. On designated visits, PGIS-SD and PGIC-SD should be recorded after the SD NRS and sleep diary in the morning; PGIS-P and PGIC-P should be recorded after the PP NRS and AP NRS in the evening.
- Pruritus assessments scheduled for clinic visit days that are recorded by subjects in the evening (ie, PP NRS, AP NRS, PGIS-P, PGIC-P) will be recorded the evening before the clinic visit.
- Patient-reported outcome assessments and designated safety measurements should occur before investigator assessments, laboratory sample collections, and study drug administration.
- Optional for consenting subjects and only for selected equipped sites; see Section 11.8 for details on clinical photographs.
- Subjects with a medical history of asthma will complete the ACT testing at each scheduled visit. Subjects with de novo asthma will complete the ACT testing beginning from de novo diagnosis and at all subsequent scheduled visits.

This document is confidential.

- j) PEF testing will be performed for all subjects at screening, baseline, Week 8, Week 16, Week 24, and follow-up visits. For subjects reporting a medical history of asthma, PEF testing will be performed at all visits during the clinical study. For subjects diagnosed with de novo asthma, PEF testing will be performed at all visits, starting with the visit in which the diagnosis was confirmed. Subjects should be asked to withhold asthma medication on study visit days until after PEF testing is complete, to the extent it does not pose an undue risk to the subject. See Section 12.6.3 for details.
- k) 12-lead ECGs should be performed in the supine position, before any scheduled vital sign measurements and blood draws. See Section 12.4.
- l) In case of indeterminate result for TB test, the test should be repeated (only 1 retest is allowed). If the test is still indeterminate, the subject must not be included in the study, unless subject has a documented history of completion of an appropriate TB treatment regimen with no history of re-exposure to TB since their treatment was completed.

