8.2. Key Definitions

Screening period is a period of up to 4 weeks before Baseline/Day 1 during which subject eligibility is evaluated. Subjects receiving rescue therapies during the screening period are not eligible to participate in the study.

The 24-week **treatment period** is defined as Baseline/Day 1 to Week 24. If early discontinued during treatment period, it is defined as the period until 4 weeks (<=28 days) after last dosing date or early termination date whichever is earlier.

Follow-up period is defined as the post end of treatment period to follow-up visit in respective treatment period.

The **Baseline value** is defined as the last non-missing value before the first dose of study drug. In case that the date of first injection is not available, the date of randomization is considered.

For diary data (PP NRS, SD NRS), the Baseline values will be derived from data collected during the 7 days prior to the first administration of study drug, if subject is treated. Otherwise, the data collected during 7 days prior to randomization will be used. Baseline score will be the weekly prorated average of non-missing subject diary scores reported during the 7 days. A minimum of 4 daily scores out of the 7 days is required to calculate the weekly prorated average score. If there are less than 4 non-missing assessments in the baseline diary window, the interval lower bound can be extended up to 7 additional days, one day at a time, to obtain the most recent 4 non-missing values. For sensitivity analysis, a minimum of 2 or 3 daily scores out of the 7 days will be used to calculate the weekly prorated average score for primary and key secondary endpoints and the interval will not be extended with additional days.

The **date of first treatment** is defined as the date of first injection of study drug.

The **date of last treatment** is defined as the date of last injection of study drug.

Study day is defined as the number of days from the date of first treatment (randomization date if not treated) and will be calculated as follows:

- If the event date \geq date of first treatment, then study day = event date - date of first treatment + 1. Treatment Day 1 is therefore defined as the day of first treatment.

This document is confidential.

- If the event date < date of first treatment, then study day = event date - date of first treatment.

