10.3.3. Pruritus Numeric Rating Scale (NRS)

The Pruritus NRS is a scale to be used by the subjects to report the intensity of their pruritus (itch) during the last 24 hours. Peak pruritus (PP NRS) is an assessment of the maximum itch intensity in that period while average pruritus (AP NRS) provides a measure of overall pruritus intensity.

Subjects will be asked the following question:

- For maximum itch intensity (PP NRS): "On a scale of 0 to 10, with 0 being 'no itch' and 10 being the 'worst itch imaginable', how would you rate your itch at the worst moment during the previous 24 hours?"
- For average itch intensity (AP NRS): "On a scale of 0 to 10, with 0 being 'no itch' and 10 being the 'worst itch imaginable', how would you rate your itch overall during the previous 24 hours?"

The screening PP/AP NRS will be determined by a single assessment using the PP/AP NRS (score ranging from 0 to 10) for the 24-hour period immediately preceding the screening visit.

The Baseline PP/AP NRS will be determined based on the average of daily PP/AP NRS (score ranging from 0 to 10) respectively during the 7 days immediately preceding Baseline (rounding to nearest whole number is not permitted). A minimum of 4 daily scores out of the 7 days immediately preceding Baseline (up to one day before date of first treatment) is required for this calculation. If there are less than 4 non-missing assessments in the baseline diary window, the interval lower bound can be extended up to 7 additional days, one day at a time, to obtain the most recent 4 non-missing values.

PP/AP NRS at all follow-up visits will be determined in the same manner, however if the intake date of rescue therapy is before and on the last day of the weekly visit window, this week will be treated as treatment failure except for OC analysis and the weekly average will be imputed using the worst case value, see [Section 8.3](#).

Subjects will receive instructions on how to record their PP/AP NRS scores and will complete the assessment once daily in the evening throughout the clinical study (including the run-in and the follow-up period).

PP NRS will be determined by an average as described above at every week from Baseline to Week 24 as a continuous variable.

Descriptive summary of PP NRS will be provided on the ITT and PP populations using observed cases. Absolute change and percentage change from Baseline for the PP NRS will also be included in the summary on the ITT and PP populations.

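### The fixed Week 24 diary window leaves subjects seen 4 to 7 days early, within the permitted visit window, with fewer than the 4 scores needed, so they count as Week 24 non-responders

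*SAP*

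**What the plan says.** **Window.** SAP Section 8.4 assigns evening diary data (PP NRS, AP NRS) to visits by "considering the data during the 7 days immediately preceding the target study day of analysis visit"; the morning diary (SD NRS, sleep diary) uses the 7 days up to the target day. With a target of Day 169, Table 8-2 gives Days 162-168 and 163-169 for Week 24.

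**Visit and end of diary.** Table 4-2 (Section 4.6) sets the Week 24 visit at Day 169 ±7. Its notes have "PP NRS and AP NRS to be recorded by subjects once daily in the evening (Visit 1/Screening through Visit 8/Week 24"), and the morning items, if possible, "within 1 hour of getting out of bed (Visit 1/Screening through Visit 8/Week 24"). Evening pruritus scores due on a clinic day "will be recorded the evening before the clinic visit".

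**Minimum and extensions.** Section 8.2 states: "A minimum of 4 daily scores out of the 7 days is required to calculate the weekly prorated average score". Section 10.3.3 derives later PP/AP NRS values in the same way as baseline, and Section 10.3.4 sends later SD NRS values to Table 8-2. Footnote a to that table extends the baseline window. Footnote b, which opens "If there are less than 4 assessments during Week 16 visit window, upper bound of the visit window", extends Week 16. Week 24 has no footnote.

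**Missing values.** Section 8.3: "All missing values will be treated as a non-responder for the binary endpoints for primary, key secondary and secondary endpoints".

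**A conflicting statement.** Section 10.3.3 says that PP/AP NRS is completed "once daily in the evening throughout the clinical study (including the run-in and the follow-up period").

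**The concern.** At earlier visits an early attendance costs nothing, because the diary continues and fills the nominal week. On the schedule's own notes, Week 24 is where collection stops. A subject who attends on a permitted early day can therefore lack a Week 24 weekly mean without having missed a single entry.

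In the binary endpoints this missing value is scored as treatment failure, so a scheduling fact becomes an efficacy outcome. The same subject's IGA from that visit is accepted as Week 24, since Table 8-1 allows Days 155-210. In the joint PP NRS and IGA endpoint, a true responder on both components would fail solely because of the diary window.

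Section 4.1 says that the 8 weeks after Week 16 were added to provide further data requested by the European regulator. The Week 24 results should therefore not depend on appointment dates.

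**Working it through.** **Inputs.** Target day T = 169, visit range 162-176 and diary end at the visit (Table 4-2 and notes); windows from Table 8-2; minimum of 4 scores (Section 8.2).

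**Reproducing the plan's windows.** Evening: T-7 to T-1 = 162 to 168. Morning: T-6 to T = 163 to 169. Both match Table 8-2.

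**Entries available.** Take a visit on Day V, from 162 to 169, with a complete diary. The last evening entry is Day V-1 and the last morning entry is Day V.
- Evening entries in the window: (V-1) - 162 + 1 = V - 162.
- Morning entries in the window: V - 163 + 1 = V - 162.

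| Visit day | Days early | Entries | At least 4? |
|---|---|---|---|
| 169 | 0 | 7 | yes |
| 168 | 1 | 6 | yes |
| 167 | 2 | 5 | yes |
| 166 | 3 | 4 | yes, with no missed day |
| 165 | 4 | 3 | no |
| 164 | 5 | 2 | no |
| 163 | 6 | 1 | no |
| 162 | 7 | 0 | no |

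Four of the 15 permitted visit days therefore give a missing Week 24 mean despite full compliance.

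**Size.** The SAP gives no distribution of visit dates, so the share f of subjects seen on Days 162-165 is an assumption. The rates of 50% and 20% are borrowed from the Week 16 planning in Section 4.3 purely for illustration. If f is equal in both arms and unrelated to response, each rate is multiplied by (1 - f):

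| f | Nemolizumab | Placebo | Difference (points) |
|---|---|---|---|
| 0 | 50.0% | 20.0% | 30.0 |
| 2% | 49.0% | 19.6% | 29.4 |
| 5% | 47.5% | 19.0% | 28.5 |
| 10% | 45.0% | 18.0% | 27.0 |
| 4/15 = 26.7% | 36.7% | 14.7% | 22.0 |

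The last row assumes visits spread evenly over the 15 days, so that 7 days early is as likely as on time. It is an extreme.

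**Would a window extension help?** Extending the upper bound adds nothing, because the diary has ended: the counts stay at 3, 2, 1 and 0. Extending the evening lower bound by 5 days, to Day 157, gives (V-1) - 157 + 1 = V - 157 entries, that is 8, 7, 6 and 5 for visits on Days 165, 164, 163 and 162. The morning count with lower bound Day 158 is the same. All four reach 4.

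**The case against.** **The end of the diary is not settled.** Section 10.3.3 has PP/AP NRS continuing into follow-up. If that is right, subjects who do not enter the long-term extension lose no PP/AP NRS data. This stands as a limit on the finding, and the SAP alone does not show which statement is right. It does not help SD NRS, for which no follow-up collection is stated, or subjects entering the extension, who have no follow-up visit.

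**An extension might carry over.** Section 10.3.3 gives the baseline rule, including its lower-bound extension, and then derives later PP/AP NRS values likewise. Read broadly, this would rescue Week 24. The narrower reading is stronger: the extension is worded for the baseline window and Week 16 has its own rule. Some ambiguity remains for PP/AP NRS, but not for SD NRS.

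**Companion analyses would show the effect.** Observed-case proportions are planned for all three scales, and LOCF for PP NRS, where a full Week 23 could be carried forward. A minimum of 3 scores recovers Day 165 and a minimum of 2 recovers Days 164-165, for the PP NRS and SD NRS endpoints to which these rules apply. None of this repairs the CMH comparison, which uses non-responder imputation, and Days 162-163 are never recovered by the lower minimum.

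**Stronger readings.** A reader might infer bias in the MI and MMRM analyses. If the loss follows scheduling rather than response, it is compatible with missing at random and costs precision only. A reader might also infer that one arm comes in early to enter the extension study. The trial is double-blind and nothing in the SAP supports that.

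**Conclusion.** The defect is real and limited. As written, a compliant subject seen on Days 162-165 cannot have a Week 24 diary mean, provided that the diary ends at the visit as the Table 4-2 notes say. That subject is a non-responder in the Week 24 binary endpoints for PP NRS, AP NRS and SD NRS and in the joint PP NRS and IGA endpoint. The subject is missing in the continuous ones, which go to MI or MMRM, or to observed-case summaries for the sleep diary.

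Both primary and all five key secondary endpoints are at Week 4 or Week 16 and are unaffected. The affected endpoints lie outside the fixed testing sequence of Section 10. With equal visit timing in both arms, both rates and their difference shrink. At the assumed shares of 2-10%, the illustrative loss is 0.6 to 3.0 points out of 30. The true share cannot be obtained from the SAP.

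**What to change.** Add a Week 24 footnote to Table 8-2. If the Week 24 visit took place before Day 169 and fewer than 4 entries fall in the window for that reason, extend the lower bound one day at a time, by up to 5 days as for Week 16, until the most recent 4 entries up to the actual visit are reached. Subjects seen on Days 166-168 with complete diaries already have 4-6 entries and keep their present derivation.

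Reconcile the Table 4-2 notes with Section 10.3.3 on when PP/AP NRS collection ends.

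The cost is one footnote, a small derivation change and one textual correction, all of which can be settled blind before database lock. The downside is that the Week 24 value for these subjects reuses Week 23 diary days. With a complete diary, 1, 2, 3 or all 4 of the 4 entries come from Week 23 for visits on Days 165, 164, 163 and 162. The footnote should say so, and the number of subjects derived this way should be reported by arm.
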